3.4 Withdrawals and Discontinuation from Study

Participation in the study is strictly voluntary. Participants have the right to withdraw from the study at any time and for any reason, without penalty or prejudice to further treatment. The Principal Investigator and/or designee may, at their own discretion, terminate a subject from continuing in the study if it is considered to be in the participant's best welfare, or if the participant is not willing or able to comply with the study requirements. The reason for withdrawal or termination will be documented. Study participants may voluntarily withdraw their consent for participation at any time and for any reason, without penalty. A study participant may be withdrawn from the study for the following reasons:

- Medical illness or a new clinical finding which in the opinion of the investigator could compromise the safety of the subject or interfere with the evaluation of the safety, tolerability, or immunogenicity of the study products.
- The subject no longer meets eligibility criteria.
- As deemed necessary by the investigator for non-compliance or other reasons.
- Subject lost to follow-up.
- Termination of the study.
- New information becomes available that makes further participation unsafe.

Handling of Participant Withdrawal or Termination. Every effort will be made to undertake protocol-specified safety follow-up procedures to capture AEs, serious adverse events (SAEs), and unanticipated problems (UPs). In the event of withdrawal or termination from the study, reasonable efforts should be made to conduct the following procedures:

- Review diary card/ memory aid, if still in use prior to withdrawal
- Updating any ongoing AE/SAEs that remain ongoing at time of subject's last visit prior to withdrawal
- Query about AEs, SAEs and concomitant medications if the interval between the subject's last visit and the time of withdrawal is within the protocol defined reporting period
- Targeted physical examination, if there are any ongoing AEs at the time of withdrawal
- Blood for safety laboratory testing, if withdrawal occurs before the day 8 visit
- Update contact information

4 INVESTIGATIONAL PRODUCTS

4.1 Description of Investigational Products

4.1.1 Trivalent, with preservative (multi-dose vials)

This study product consists of a cGMP lot of a trivalent *S. Enteritidis*/*S. Typhimurium*/*S. Typhi* Vi conjugate vaccine consisting of a 1:1:1 mix of *S. Enteritidis* COPS linked to Phase 1 *Enteritidis* flagellin (FliC) subunits and *S. Typhimurium* COPS linked to Phase 1 *Typhimurium* flagellin (FliC) subunits, plus Typbar TCV® (*S. Typhi* Vi capsular polysaccharide linked to tetanus toxoid protein). The study product is presented in multi-dose vials containing 2-phenoxyethanol preservative.

4.1.2 Placebo

The placebo consists of the buffer vehicle in which the conjugate vaccines are suspended, with 2-phenoxyethanol preservative.

4.2 Formulation, Storage, Packaging, and Labeling

4.2.1 Trivalent, with preservative (multi-dose vials)

Each vial holds 2.5 mL (plus overfill) of material for which a 0.5 mL volume contains *S. Enteritidis* 25 µg (by polysaccharide weight), *S. Typhimurium* 25 µg (by polysaccharide weight), and *S. Typhi* Vi 25 µg (by polysaccharide weight) conjugate vaccine, plus Tween-80 and PBS, and 2-phenoxyethanol preservative. Each multi-dose vial is to be stored between 2-8°C, not to be frozen.

4.2.2 Placebo

Each vial holds 2.5 mL (plus overfill) of material for which a 0.5 mL volume contains PBS, Tween-80, plus 2-phenoxyethanol preservative. Each multi-dose vial of placebo is to be stored between 2-8°C, not to be frozen.

4.3 Preparation and Administration

Step 1 (Cohort A). For each dose of vaccine, a 0.25 mL volume from a vial containing study product is to be mixed with 0.75 mL of placebo (PBS, Tween-80, and 2-phenoxyethanol). After mixing, 0.5 mL should be withdrawn into a 1 mL syringe -- this volume should contain ~6.25 µg of product (by polysaccharide weight) as a dose in 0.5 mL. The 0.5 mL of placebo will contain only buffer and preservative.

Step 2 (Cohort B) and Cohort C. For each dose of vaccine, a 0.5 mL volume from a vial containing study product is to be mixed with 0.5 mL of placebo (PBS, Tween-80, and 2-phenoxyethanol). After mixing, 0.5 mL should be withdrawn into a 1 mL syringe-- this volume should be equivalent to ~12.5 µg of test product (by polysaccharide weight) dose in 0.5 mL. The 0.5 mL of placebo will contain only buffer and preservative.

Step 3 (Cohort C). For each dose of vaccine, a 0.5 mL volume from a vial containing study product is to be directly withdrawn into a 1 mL syringe-- this should be equivalent to ~25 µg (by polysaccharide weight) dose in a volume of 0.5 mL. The 0.5 mL of placebo will contain only buffer and preservative.

The diluted study product vial can be used up to 4 hours, if stored at 2-8 °C, or up to a maximum of 30 minutes if kept at room temperature. Prepared diluted vaccine must be manually shaken gently before using. Once the mixed vaccine has been drawn into a syringe, it should be administered within 30 minutes. Any unused vaccine or waste material should be disposed of in accordance with local requirements.

Each vial (holding 2.5 mL of material plus overfill) shall only be used to withdraw a maximum of 5 doses (5 punctures per vial) for each day of scheduled administration. Each multidose vial will only be used for one day. At the end of each vaccination day, unused vaccine in the multidose vial will be marked as un-useable. The Pharmacy will be responsible for keeping track of the number of doses drawn per vial and maintaining proper investigational product accountability on the accountability log.

4.4 Study Product Accountability

The study product will be stored in and dispensed by the University of Maryland Medical Center (UMMC) Investigational Drug Service (IDS) pharmacy or Pharmaron. The FDA requires accounting for the disposition of all investigational products. The Investigator is responsible for ensuring that an accurate record of product disposition is maintained and product is dispensed only by authorized personnel as required by applicable regulations and guidelines. Records of product disposition as required by federal law consist of the date received, date administered, quantity administered, and the subject number to whom the study product was administered. The investigational pharmacist will be responsible for maintaining accurate records of the shipment and accountability of the study product.

For participants enrolled at CVD, the preparation and dispensing of the study product is performed by the IDS Pharmacy and the dosing of subjects is performed by CVD research staff; the process and procedures are documented and maintained in a secure location that is segregated from the blinded research staff. Participants enrolled at Pharmaron will have the study product preparation and administration according to their internal standards. The pharmacy records (IDS pharmacy, CVD, and Pharmaron) will be made available for inspection by external monitors and by the relevant regulatory agencies (e.g., FDA) at any time.

4.5 Masking of the Study Product

A prospectively assigned vaccinator and checker will be designated as unblinded personnel and will not have any role in the assessment of adverse events in study participants. Unblinded personnel will be responsible for the preparation of the study products and for the blinded labeling of the study products. The unblinded staff will be responsible for maintaining the randomization key and will secure these study documents in a locked cabinet.

The PI or the Data and Safety Monitoring Board must submit a written request, to inform each other, for emergency unblinding, if this were to be performed. The written request must clearly state the justification for the emergency unblinding and describe which specific participants are to be unblinded. This document will be filed in the study regulatory file.

5 STUDY PROCEDURES

5.1 Clinical Evaluations

Medical History: Will be obtained by interview of the participants. Participants will be queried regarding a history of significant medical disorders of the head, eyes, ears, nose, throat (HEENT), mouth, cardiovascular system, lungs, gastrointestinal tract, liver, pancreas, kidney, urologic, nervous system, blood, lymph glands, endocrine system, musculoskeletal system, skin, and genital/reproductive tract. A history of any allergies, cancer, immunodeficiency, psychiatric illness, substance abuse, and autoimmune disease will be solicited.

Medication History: All current medications and medications taken in the 28 days prior to enrollment (prescription and over-the-counter drugs will be included as well as vitamins and supplements) through 28 days after the last vaccination or early termination (if prior to 28 days from last vaccination), whichever occurs first. Assessment of eligibility also will include a review of permitted and prohibited medications (per the exclusion criteria).

Physical Examination: At screening appropriate study personnel will record oral temperature, pulse and blood pressure and perform a focused physical examination to assess general wellness which will include the following areas/systems: HEENT; lymph nodes; skin; pulmonary; cardiovascular; abdominal; neurological; and musculoskeletal systems. The physical examination should specifically address issues identified by the medical history of the participant. At following visits including enrollment, oral temperature, pulse, and blood pressure will be recorded and a targeted physical examination may be conducted if indicated based on review of medical history.

Reactogenicity Assessments: Will include brief history for assessment of AE/SAEs just prior to and following vaccination (Day 1 for Cohorts A-B and Days 1 and 29 for Cohorts C and D), which includes an assessment of systemic and local reactions. Participants will be observed in-clinic for 20 minutes following each vaccination.

Memory Aids: All participants will complete a subject memory aid distributed after each vaccination. Subject memory aids will be reviewed with the participant for AE/SAEs during visits occurring 7 days after each dose of vaccine. Following review, the appropriate case report form (CRF) will be completed by the study staff. Memory aids will not be retained as a source document.

5.2 Clinical Laboratory Evaluations

A total of 16 mL blood will be collected for screening clinical labs for the evaluation of eligibility. If screening laboratory results are out of range value, they may be repeated once provided there is an alternative explanation for the out of range value. Participants must have acceptable screening laboratory findings prior to enrollment. The acceptable ranges for study eligibility are listed in Appendix B.

For the assessment of safety, a total of 12.5 mL of blood will be collected for clinical safety labs on Day 1 (pre-vaccination) and the Day 8 (7-days post dose #1) visit. This evaluation is to include a CBC with differential for total white blood cells (WBC) count, hemoglobin (Hg), absolute neutrophil count (ANC), platelet count, creatinine, aspartate aminotransferase (AST),

alanine aminotransferase (ALT), total bilirubin (TBIL), and C-reactive protein (CRP). On Day 2 (one day after receipt of the first dose of vaccine), a 3.5 mL volume of blood will be collected for the assessment of C-reactive protein only. The grading of toxicity for the clinical safety lab values that are not in the normal range is provided in Appendix C.

Due to the U.S. Public Health Emergency with COVID-19, SARS-CoV-2 testing will be performed on the days of scheduled vaccination. These test results are not intended to inform the eligibility of participants for vaccination, as the results are likely to be available after 2-3 days. However, for possible pre-symptomatic participants (i.e., eligible due to the absence of symptoms at the time of vaccination) the positive test result could be used to provide an alternate etiology for the development of symptoms due to COVID-19 rather than due to the study product. The test results of acute infection (positive PCR) or prior infection (positive antibody) will also be used in planned stratified analysis of the immunology outcomes, as COVID-19 infection may alter the immune response to vaccination. The results of SARS-CoV-2 testing will be provided to participants at their Day 7 and Day 36 visits. If SARS-CoV-2 testing results are received prior to these visits, the research team may call participants to report these results.

All women of child-bearing potential will have a serum pregnancy test performed during screening and a urine pregnancy test on the vaccination days. The results of the urine pregnancy test must be negative prior to enrollment in the study, and prior to each vaccination.

When a result is abnormal and satisfies the toxicity grading scale, the result must be recorded as a laboratory AE and followed until resolution or it becomes stable. If a laboratory value is abnormal but does not satisfy the toxicity grading scale, then the abnormality must be assessed by the site PI or designee for clinical significance. For all clinically significant abnormalities or grade 1 or higher abnormalities, the value should be recorded as a laboratory AE. Any grade 2 or higher abnormality must be followed until resolution, it becomes stable, or it becomes grade 1 or lower.

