2.4 Secondary Objectives and Outcome Measures

The secondary objectives and outcome measures of this study are the following:

1. Safety: To assess the frequency and severity of abnormalities in clinical safety laboratory parameters at 7 days following the first dose of vaccine.
2. Immunogenicity: To measure the proportion of subjects that achieve a four-fold increase in titer, as compared to baseline, of specific serum IgG anti-COPS (S. Enteritidis or S. Typhimurium), anti-Vi (S. Typhi) polysaccharide, and anti-FliCn (S. Enteritidis or S. Typhimurium) antibody at day 180/210, as measured by ELISA.
3. Immunogenicity: To calculate the GMT of serum IgG anti-COPS (S. Enteritidis or S. Typhimurium), anti-Vi polysaccharide, and anti-FliC (S. Enteritidis or S. Typhimurium) antibodies at days 1, 29, 57, and 180/210, as measured by ELISA.

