7.2 Methods and Timing for Assessing, Recording, and Analyzing Safety Parameters

Adverse Event (AE): ICH E6 defines an AE as any untoward medical occurrence in a patient or clinical investigation subject administered a pharmaceutical product regardless of its causal relationship to the study treatment. An AE can therefore be any unfavorable and unintended sign (including an abnormal laboratory finding), symptom, or disease temporally associated with the use of medicinal (investigational) product. The occurrence of an AE may come to the attention of study personnel during study visits and interviews of a study recipient presenting for medical care, or upon review by a study monitor.

All AEs including local and systemic reactions not meeting the criteria for "serious adverse events" should be captured on the appropriate CRF. Information to be collected includes event description, time of onset, clinician's assessment of severity, relationship to study product (assessed only by those with the training and authority to make a diagnosis, which would include MD, PA, and Nurse Practitioner, listed on the FDA Form 1572), and time of resolution/stabilization of the event. All AEs occurring while on study must be documented appropriately regardless of relationship. All AEs will be followed to adequate resolution.

Any medical condition that is present at the time that the patient is screened should be considered as baseline and not reported as an AE. However, if it deteriorates at any time during the study, it should be recorded as an AE.

Special Circumstance of COVID-19 Pandemic. While there is a U.S. Public Health Emergency for COVID-19, there is the risk of community transmission of infections. The testing of both anti-SARS-CoV-2 antibody and presence of virus by PCR on the days of vaccination (both dose #1 and #2) are intended to provide the investigators with information on potential asymptomatic or presymptomatic infections at vaccination, but the results will not be available in time prior to vaccination. Therefore, the results are intended to potentially provide alternate etiology for reactogenicity that might be observed post-vaccination which could be due to a COVID-19 infection rather than to the study product. The results of SARS-CoV-2 testing will be provided to participants at their Day 7 and Day 36 visits. If SARS-CoV-2 testing results are received prior to these visits, the research team may call participants to report these results.

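### Some eligible baseline laboratory values are already Grade 1, and the plan does not say whether an unchanged one counts as a Day 8 abnormality

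*Combined protocol and SAP*

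**What the plan says.** Section 5.2 gives the recording rule twice. First: "When a result is abnormal and satisfies the toxicity grading scale, the result must be recorded as a laboratory AE". Then, with Grade 1 named: "For all clinically significant abnormalities or grade 1 or higher abnormalities, the value should be recorded as a laboratory AE". Neither sentence excepts a value that was already abnormal before the injection.

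Section 7.2 has a general baseline rule: "Any medical condition that is present at the time that the patient is screened should be considered as baseline and not reported as an AE". It continues: "However, if it deteriorates at any time during the study, it should be recorded as an AE".

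Secondary objective 1 (Section 2.4) is "To assess the frequency and severity of abnormalities in clinical safety laboratory parameters at 7 days following the first dose of vaccine". It does not say whether an abnormality must be new or worse than before vaccination.

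Sections 5.2 and 7.1 provide for safety laboratories on Day 1 before vaccination and again on Day 8, with an extra CRP on Day 2. Section 10.2 tabulates AEs by body system and preferred term. It specifies no separate display for laboratory values.

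**The concern.** The objective is meant to show what happens to laboratory values after the first dose. If a participant enters with a Grade 1 value and still has it on Day 8, that value describes the participant and not the vaccine. Whether it is counted depends on which section the site follows, and two sites enrol.

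The placebo group cannot supply a reliable background rate. Each Part 1 cohort has 2 placebo recipients, 6 in all, and the synopsis says that Cohort D may not be conducted. The best control available is the participant's own Day 1 value. CRP deserves particular care: Section 1.4 links raised CRP to flagellin-containing vaccines, and part of its eligible range is already Grade 1.

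**Working it through.** The plan states no figure on this point, so there is none to reproduce. The check lays the eligibility limits of Appendix B over the grade limits of Appendix C.

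**Inputs.** Reference and eligible ranges come from Appendix B, and grade multiples from Appendix C. I take the Appendix B reference limits as LLN and ULN (assumption). Only values outside the reference range are graded, following Section 5.2: "The grading of toxicity for the clinical safety lab values that are not in the normal range is provided in Appendix C".

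**Formula.** A value is eligible and already Grade 1 if it lies outside the reference range, inside the eligible range, and short of the Grade 2 limit (multiple × LLN or ULN).

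| Analyte | Reference limit | Eligible limit | Grade 2 limit | Eligible and Grade 1 |
|---|---|---|---|---|
| Haemoglobin low, men (g/dL) | 13.5 | 11.0 | 0.8 × 13.5 = 10.8 | 11.0-13.4 |
| Haemoglobin low, women | 12.0 | 10.3 | 0.8 × 12.0 = 9.6 | 10.3-11.9 |
| Haemoglobin high, men | 17.5 | 17.6 | 1.2 × 17.5 = 21.0 | 17.6 only |
| Haemoglobin high, women | 16.0 | 17.6 | 1.2 × 16.0 = 19.2 | 16.1-17.6 |
| Platelets low (×10³/mm³) | 130 | 125 | 0.9 × 130 = 117 | 125-129 |
| Platelets high | 400 | 480 | 1.3 × 400 = 520 | 401-480 |
| ALT (U/L) | 45 | <68 | 2.5 × 45 = 112.5 | 46-67 |
| AST, men (U/L) | 40 | <60 | 2.5 × 40 = 100 | 41-59 |
| AST, women | 30 | <45 | 2.5 × 30 = 75 | 31-44 |
| Total bilirubin (mg/dL) | 1.2 | <1.5 | 2.0 × 1.2 = 2.4 | 1.3-1.4 |
| CRP (mg/dL) | <0.8 | <1.1 | 2.0 × 0.8 = 1.6 | 0.8 to <1.1 |

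**Little or no overlap.** For creatinine the band is above 1.3 to below 1.4 in men and above 1.1 to below 1.2 in women, which is empty at one decimal. WBC overlaps only at exactly 3.0 or 11.5, and high ANC only at 8900-8910. Low ANC does not overlap, because eligible values start at 1100 and Grade 1 ends at 1000.

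**Halting rule.** In every row the eligible limit stops short of the Grade 2 limit. Section 7.3 requires the same Grade 2 or greater abnormality in two or more subjects of a dosage cohort, judged associated with vaccine. An unchanged eligible value cannot meet it.

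**Weight of one event.** One participant with an unchanged Grade 1 value adds 1/8 = 12.5 percentage points in Cohort A vaccinees, 1/10 = 10 in Cohort B, and 1/12 = 8.3 among the 6 + 6 recipients of 25 µg in Cohort C. These are the sizes of a single event. They do not estimate how many occur.

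**Placebo background.** With no events among n recipients, the two-sided exact 95% upper limit is 1 - 0.025^(1/n). For n = 2 this is 84%; for n = 2 + 2 + 2 = 6 it is 46%.

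**Which baseline.** Section 7.2 refers to screening, which Section 6.1 places from Day -45 to Day -2. Section 7.1 places the laboratory baseline before vaccination. A value normal at screening and Grade 1 on Day 1 before the injection falls outside the Section 7.2 exclusion, yet it cannot be a vaccine effect.

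**The case against.** The strongest reply is that Section 7.2 already answers the point. Its AE definition covers "any unfavorable and unintended sign (including an abnormal laboratory finding), symptom, or disease temporally associated with the use of medicinal (investigational) product", so its baseline rule can reasonably be read to cover laboratory values too. A reader might infer from Section 5.2 alone that unchanged values are certain to be counted as AEs. Section 7.2 prevents that from being treated as settled. It does not resolve the matter either: it speaks of a medical condition, uses screening as its reference, leaves deterioration undefined for a laboratory value, and does not define the Day 8 endpoint.

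A second reply is that Section 5.2 governs data capture, that causality is assessed separately, and that Section 10.2 openly prefers over-calling safety events. This is fair, and nothing bars the sponsor from showing Day 8 against Day 1. But no such display is planned, and a count without one cannot separate entry status from change.

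A third reply is that counting only rises in grade would hide real worsening. This stands. ALT rising from 46 to 112 U/L, or haemoglobin in a man falling from 13.4 to 10.9 g/dL, remains Grade 1 throughout. A grade-increase count must therefore not replace the count of all graded values.

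A reader might also infer a threat to dose escalation. The documents do not support that: the halting rule needs Grade 2, and the go/no-go criteria in Section 10.3 use solicited events.

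**Conclusion.** The point holds as an unreconciled conflict between Sections 5.2 and 7.2, together with an endpoint that does not say how a pre-existing abnormality is handled. It concerns sub-ranges of haemoglobin, platelets, ALT, AST, bilirubin and CRP, not eligible values in general. Under Section 5.2 as written, an unchanged value in one of those bands adds to the Day 8 count.

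The consequence is limited to Grade 1 counts in descriptive tables of a trial with no powered comparison. It is tempting to attach an expected rate of spurious abnormalities. The documents give no prevalence for these bands and no correlation between analytes, so any such rate would rest wholly on assumption. The conclusion assumes that the Appendix B reference limits serve as LLN and ULN. The statement about Grade 2 applies to values unchanged from an eligible screening result.

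**What to change.** Reconcile Sections 5.2 and 7.2. State which rule governs a graded laboratory value present before vaccination, which sample is the baseline, and what deterioration means for a laboratory value.

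For secondary objective 1, keep the count of all graded Day 8 values and add:

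- (a) the count of values whose grade is new or higher than the participant's own Day 1 pre-vaccination grade;
- (b) a Day 1 to Day 8 grade shift table by dosage;
- (c) the change in value from Day 1, so that worsening within a grade stays visible.

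Show CRP for Days 1, 2 and 8 as a supporting display, since Day 2 lies outside the 7-day objective. Give the SMC the Day 1 value beside each graded value.

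The cost is one sentence and one table. The Day 1 samples are already in the schedule, so no new data are needed, and no eligibility limit or halting rule changes.
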